### **3.2 Study sites**

The Seattle Malaria Clinical Trials Center (MCTC) is an inter-institutional collaboration based primarily at the Fred Hutch Cancer Research Center and the University of Washington. For this study, clinic visits will be conducted at the Fred Hutch Prevention Center in the Arnold Building. The Prevention Center is a fully-equipped outpatient clinical research facility with exam rooms, a laboratory, pharmacy, dining area, and adequate office spaces. The center is staffed by a full-time staff capable of conducting all study procedures listed herein. Blood samples to be tested at the point of care will be tested in the Prevention Center clinical laboratory.

The University of Washington Department of Laboratory Medicine will provide reference laboratory services. Hemoglobin and G6PD reference testing will be performed at the Department's laboratories at the University of Washington Medical Center and/or Northwest Hospital. Mayo Medical Laboratories will serve as a backup send out laboratory for the G6PD test. All laboratories perform the Pointe Scientific G6PD assay and are CLIA/CAP certified.

Frozen blood samples not used by clinical or POC testing will be stored

## **4. Research participants**

### **4.1 Characteristics of research participants**

This study will involve healthy adult patients aged 18-65 years old capable of providing informed consent.

### **4.2 Inclusion and exclusion criteria**

#### **4.2.1 Patients**

Criteria for inclusion of patients:

- Age 18-65
- Healthy volunteer by self-report
- Willingness to provide consent

Criteria for exclusion of patients:

- Blood transfusion in the past 90 days by self-report
- Pregnancy by self-report

## **5. Study procedures**

### **Recruitment and screening at Seattle Malaria Clinical Trials Center**

Up to 250 adult subjects meeting eligibility criteria will be included in this study. Subjects will be recruited from the greater Seattle area through a variety of Institutional Review Board (IRB)-approved messaging and outreach methods via the MC-002 general screening protocol (IR# 8366). Recruitment methods will target populations with expected

[figure not shown]
high prevalence of G6PD deficiency, including Southeast Asian populations and African-American populations. This will be achieved through outreach with community care facilities in the University of Washington network.

Screening procedures include the informed consent process and obtaining a brief history. The history will include questions regarding ethnicity, age, sex, and current health status. The screening/enrollment visit will take place at the Prevention Center clinic at the Fred Hutch Cancer Research Center. Subjects may be enrolled the same day that the informed consent procedure occurs. Subjects may also be invited to consent to be included in the database maintained for Seattle MCTC activities under the IRB-approved MC-002 general screening protocol and/or in the asymptomatic malaria infection study MC-005. The informed consent will include a provision that the reference laboratory G6PD result for subjects enrolled in MC-005 will be added to the MC-005 study database.

### **Sample testing at Seattle Malaria Clinical Trials Center and the UW Department of Laboratory Medicine**

See Figure 1 for a summary of tests to be performed on the samples.

Figure 1. Diagnostic performance assessment process

Abbreviations: EDTA, ethylenediaminetetraacetic acid; G6PD, glucose-6-phosphate dehydrogenase; Hb, hemoglobin; ml, milliliter.

As noted in Table 3 below and Figure 1, volunteers will come to the clinic site, undergo the informed consent process, provide written informed consent, undergo blood draw and finger stick procedures.

Table 2. Summary of study procedures.

Participant group	List of study procedures	Estimated time	Appendices
Adults	
 
Written informed consent
 
Blood draw
 
POC tests
 
	
 
30 min
 
	
 
Appendix A participant informed consent form
 
Appendix B case report form
 

## 5.1 Diagnostic performance assessment

### 5.1.1 Blood collection and testing procedures at the point of care

Following completion of the informed consent process, the study staff, who are trained in phlebotomy, will draw the following blood volumes:

- two 2-mL of ethylenediaminetetraacetic acid (EDTA)-anticoagulated blood
- one 4-mL tube of ethylenediaminetetraacetic acid (EDTA)-anticoagulated blood
- a finger stick sample of no more than 50  $\mu$ L obtained with lancet

The tubes will be identified using a study subject number. At the clinic site lab, study staff will conduct the SD Biosensor POC G6PD test and the POC HemoCue Hb test on both finger stick blood and on blood from the 4-mL tubes of EDTA-treated venous blood. Results of the in-clinic performed POC tests will be recorded on data collection forms. If an invalid test result is obtained from the finger stick sample, a second finger stick sample will be obtained, and a second test will be run. If an invalid test result is obtained from a second finger stick, the results will be recorded as invalid. If the participant is found to be anemic based only on the HemoCue assay, the participant will be referred to a health care provider for follow-up and case management.

Once POC tests are completed on venous blood, the remaining blood in the 4-mL EDTA tube will be stored and transported as follows:

- Prevention center will transfer samples to PATH laboratories approximately twice per week. Leftover samples will be aliquoted and stored at PATH laboratory for possible confirmatory or additional testing. Depending on availability of additional novel malaria tests, additional assays may be run on remaining samples. Samples will be aliquoted 6 x 0.5 ml of whole blood in cryogenic tubes and stored at -80°C in the freezer. Maximum storage time is 10 years after study end. This leftover sample will be stored for possible additional testing with the fluorescent spot test (FST). Appropriate permission for additional testing relating to malaria will be obtained through the consent process.
- The two 2-mL EDTA venous blood samples will be transported to the central reference lab by courier.

### 5.1.2 Testing procedures at the reference laboratory

At the reference laboratory, hemoglobin to normalize the G6PD values will be measured according to the G6PD reference assay instructions for use. The standard procedure for the reference laboratory is to measure hemoglobin for the Pointe Scientific G6PD test using a hematology analyzer. The Pointe Scientific G6PD reference assay will be performed in duplicate within 72 hours of collection. The temperature and humidity of the laboratory at the time of testing will also be recorded.

Test operators in the reference laboratory will be blinded to the results of the POC tests obtained and recorded at the clinic site. If there is a discordance between the replicates of the reference assay greater than allowed by the target product profile [13] (greater than 2 IU/ gram), testing with the reference test will be repeated using stored venous samples when possible. If there is discordance between the index test and the reference test, testing will be repeated using stored venous samples where possible to assess whether the discordance is reproducible. Performance characteristics and the results of additional testing of samples with discrepant results will be reported as per WHO guidelines [15].

## 5.2 Specimen collection, transport, and storage

As noted in Section 5.1.2 above, the clinic site staff will collect two 2-mL and one 4-mL EDTA tubes of whole blood as well as fingerstick capillary blood samples. Clinic staff will process the blood as in Section 5.1.1. Notably, immediately after collection, whole blood in EDTA will be stored in a refrigerator or a cooler box. As early as convenient and always within 18 hours, the two 2-mL EDTA samples will be transported to the reference laboratory.

### 5.3 Test result return

Results of HemoCue POC Hb testing will be returned immediately to participants who are anemic according to UW Hb reference ranges. Study staff will relay results and counsel participants who test positive for anemia according to the IRB-approved results return script. Participants will be notified at recruitment that the study team will tell them the results of the G6PD test after confirmation by the reference assay only if they are found to be G6PD intermediate or deficient by the reference assay. Participants who are found to be G6PD normal by the reference assay will not be notified of their result. Any participants found to be G6PD intermediate or deficient will be contacted via phone and notified of their result. The study team will recommend that the participant contact their care provider for any follow-up, including possible re-testing.

The study will make use of a study key that links participant ID, name, and contact information. This key will be populated at the time of consent and enrollment. This key will be accessible only by the MCTC Manager and will be kept in a secure location, separate from the study database. This key will enable the MCTC Manager to follow up with participants who are found to be G6PD deficient or intermediate by reference assay. The study staff involved in returning results will receive dedicated training aimed at providing the necessary information and delivering it in a way that facilitates comprehension. Once all laboratory testing and confirmatory testing is complete and all appropriate participants have been notified of their test results, the study key will be destroyed.

### 5.4 User proficiency

Study staff will be trained in the use of the assays. A proficiency panel of a characterized set of samples representative of varying levels of G6PD activity and Hb will be provided to ensure study personnel are able to perform the Pointe Scientific G6PD assay, the HemoCue Hb assay, and the SD Biosensor correctly. Proficiency testing will occur prior to the start of specimen testing on the reference methods and the investigational method. Users must pass proficiency before study testing can begin. Proficiency test results will be forwarded to PATH for review. Personnel who participate in further testing must obtain 90% or better to be deemed proficient.

### 5.5 Quality Control (QC) Testing

QC results must be within specifications for any test method result to be reported. QC testing on the Pointe Scientific G6PD assay, the HemoCue Hb assay, and the SD Biosensor will be performed each day of testing.

## 6. Consent process

The informed consent process encompasses all written or verbal study information the Seattle MCTC study staff provides to the subject, before and during the trial. All informed consent discussions will be documented by the study staff in the subject's source documentation. Consent discussions include, but are not limited to, background on G6PD and rationale for this study, an overview of the study design, study procedures, requirements for participation in the trial, and risks and benefits to the subject.

Written informed consent will be obtained only by Seattle MCTC study staff trained in the protocol and designated on the study signature log, using the protocol-specific Informed Consent Form approved by the local IRB and developed and administered in accordance with Seattle MCTC policies and procedures, local IRB/IEC requirements, federal guidelines 21 CFR 50.20, 45 CFR 46.116 and the ICH E6 Guidance Section 4.8.10.

Subjects will be provided with a copy of all consent forms that they sign. The original signed and dated copy will be kept on file in their study binder, stored in locked, limited-access cabinets within the Seattle MCTC.

## 7. Study products

### 7.1 SD Biosensor STANDARD G6PD Analyzer (investigational product)

The STANDARD G6PD Analyzer (Figure 2 on the following page) is designed to measure the quantitative determination of total Hb concentration and G6PD enzymatic activity in fresh human whole blood specimens based on reflectometry assays. The test is intended to aid in the identification of people with G6PD deficiency. The test is

currently not licensed for use in the US and is considered an investigational product. System components shall be labeled in accordance with regulatory requirements, including the following statement, "For Investigational Use Only. The performance characteristics of this product have not been established."

Figure 2. SD Biosensor STANDARD G6PD Analyzer.

## 7.2 Pointe Scientific test kit (Reference Assay)

The Pointe Scientific test kit will serve as the reference assay to assess G6PD activity. Its intended use is for the quantitative, kinetic determination of G6PD in blood at 340 nm. It is designed for in vitro diagnostic use only.

- A spectrophotometer capable of measuring at 340 nm with a temperature-controlled cuvette compartment is required to perform the assay.
- To determine G6PD activity, which is reported in terms of grams of Hb or the number of red blood cells, the Hb or red blood cell count must be determined separately from performing the G6PD assay. Calculations are then performed to obtain the G6PD activity, normalized for the Hb level. For purposes of this study, the G6PD activity from the Pointe Scientific kit will be calculated in terms of grams of Hb as determined by hematology analyzer.
- US FDA cleared: k024006, Regulatory Class II, Product Code JBF.
- Performed at UW Medicine Northwest Hospital Laboratory (UW Department of Laboratory Medicine) with optional backup sent out to Mayo Medical Laboratories

## 7.3 HemoCue system

The HemoCue Hb 201+ system is designed for quantitative POC whole blood Hb determination in primary care using a specially designed analyzer, the HemoCue Hb 201+Analyzer, and specially designed microcuvettes, the HemoCue Hb 201+Microcuvettes. The HemoCue Hb 201+system is for in vitro diagnostic use only. It consists of a small portable analyzer (photometer) and plastic microcuvettes. The microcuvette serves both as a pipette and as a measuring cuvette. A blood sample is drawn into the cavity by the capillary action. The filled microcuvette is inserted into the HemoCue Hb 201+Analyzer. The measurement takes place in the analyzer, which measures the absorbance of whole blood at an Hb/HbO2 isobestic point. The system is factory-calibrated and needs no further calibration. The HemoCue is available and registered for use at the study site.

## 7.4 Fluorescent Spot Test

The fluorescent spot test (FST) or TrinityBiotech G-6-PDH Screening test is widely used for in vitro diagnosis of G6PD deficiency using whole blood or dried blood spots. The G-6-PDH Screening test is a qualitative test performed by incubating a small amount of blood with glucose-6-phosphate and nicotinamide adenine dinucleotide phosphate (NADP). Drops of the mixture are removed at 5-minute intervals, spotted on filter paper and then viewed under long-

wave ultraviolet light. Fluorescence is clearly evident in mixtures prepared from normal blood, whereas deficient samples yield little or no fluorescence. The test is affordable and produces qualitative, visual results in minutes. This test will represent a qualitative standard care test that is currently available and cleared by the FDA. The test will be performed according to PATH's guide to fluorescent spot testing for G6PD deficiency.

## 7.5 Maintenance and Storage of Study Products

Commercial assays shall be stored at recommended storage conditions as provided in the product labeling. The STANDARD G6PD test shall be stored at ambient temperature. Control material for all assays shall be stored at recommended storage conditions as provided in the product labeling.

## 8. Data and data management

### 8.1 Statistical analyses

Data will be entered into a database with built-in validation rules to minimize data entry errors. Descriptive statistical analysis, including calculating point estimates, distribution, and frequencies, will be used to summarize and characterize the study population.

#### 8.1.1 Diagnostic performance

For purposes of diagnostics for G6PD deficiency:

- A true positive: individuals who display  $\leq 30\%$  (threshold) G6PD activity in circulating venous blood as determined by a quantitative assay and in this study specifically the Pointe Scientific Cat No. G7583. (see table 2).
- A true negative: individuals who display  $> 30\%$  (threshold) G6PD activity in circulating venous blood as determined by a quantitative assay and in this study specifically the Pointe Scientific Cat No. G7583. (see table 2).

In order to investigate the performance of the assay to distinguish females with intermediate activity from female with normal activity, the sensitivity and specificity will be determined at G6PD activity thresholds of 70% and 80%. 70% refers to the threshold used in the clinical trials for tafenoquine as a cure to *P. vivax*, and 80% refers to the most recent WHO G6PD phenotype classification.

For the purposes of this study, an individual will be considered G6PD deficient (case) if they test positive by the Pointe Scientific assay. The primary success criterion will be focused on the ability to identify G6PD-deficient patients correctly, such that the SD Biosensor POC G6PD test on fingerstick blood and the Pointe Scientific assay on venous blood should both accurately identify all severely G6PD-deficient specimens (with  $<30\%$  normal) as deficient.

The performance of the POC G6PD test against the Pointe Scientific assay will be determined by calculating the sensitivity and specificity. Sensitivity and specificity of the POC G6PD assay will be calculated as per Domingo et al. [19]. In summary, an adjusted male median will be calculated for both the POC G6PD and Pointe Scientific assay; from this median, the 30%, 70%, and 80% cutoff levels for the two tests will be used to categorically define G6PD-deficient cases.

Sensitivity will be determined using the following method:

- TTP = test and true positive (positive by reference assays according to case definition and positive by the POC G6PD test).
- Fntp = false negative true positive (positive by reference assays according to case definition and negative by the POC G6PD test).
- Sensitivity =  $TTP/(TTP+Fntp)$ .

Specificity will be determined by the following method:

- TPTN = test positive true negative (negative by reference assays according to case definition and positive by POC G6PD test).
- TTN = test and true negative (negative by reference assays according to case definition and negative by POC G6PD test).
- Specificity =  $TTN/(TTN+TPTN)$ .

Sensitivity and specificity results will be reported using 95% confidence intervals.

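### Could repeat testing of discordant specimens rescue a miss under the no-miss primary criterion?

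*Combined protocol and SAP*

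**What the plan says.** Section 8.1.1 makes the primary success criterion that the POC test on fingerstick blood and the Pointe assay on venous blood "should both accurately identify all severely G6PD-deficient specimens", meaning those below 30% of normal. Case status comes from the reference assay: "an individual will be considered G6PD deficient (case) if they test positive by the Pointe Scientific assay". The cell definitions for sensitivity and specificity do not name a run, and both measures are reported with 95% confidence intervals. Section 3.1 aims for 20 deficient participants among 250.

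Three repeat rules exist.

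- **Invalid fingerstick (5.1.1).** "If an invalid test result is obtained from the finger stick sample, a second finger stick sample will be obtained". A second invalid result is recorded as invalid.
- **Reference duplicates (5.1.2).** Pointe is run in duplicate and repeated when the duplicates differ by more than 2 IU/g, whatever the POC result.
- **Index against reference (5.1.2).** "If there is discordance between the index test and the reference test, testing will be repeated using stored venous samples where possible". The stated reason is to learn whether the disagreement repeats.

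On reporting, 5.1.2 says: "Performance characteristics and the results of additional testing of samples with discrepant results will be reported as per WHO guidelines". It also says: "Test operators in the reference laboratory will be blinded to the results of the POC tests". Section 5.1.1 describes the stored blood: "Leftover samples will be aliquoted and stored at PATH laboratory for possible confirmatory or additional testing", at -80°C. Section 7.1 describes the device as measuring "G6PD enzymatic activity in fresh human whole blood specimens".

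**The concern.** A criterion that allows no misses is settled by a single specimen. If discordance means disagreement at the cut-off, every discordant deficient case is a miss. The third repeat rule then re-examines misses and leaves correct detections alone. If the repeat replaced the first result, a miss could become a detection, or a reference repeat above 30% could remove the specimen from the case group. Apparent sensitivity and specificity could then only stay the same or rise. Two analysts could reach opposite conclusions from the same data, and the reported interval would not reveal the selection.

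Two other features seem to add to this. The Pointe half of the criterion looks empty when Pointe defines the cases, which might suggest that repeat Pointe values are meant to count. And a repeat request prompted by discordance can tell a blinded reference operator that the POC test disagreed.

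**Working it through.** **Size if repeats replaced first results.** The plan gives no figure for the no-miss criterion, so there is none to reproduce.

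Inputs:

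- n = 20 deficient cases (section 3.1).
- s, the true sensitivity. Section 3.1 uses 95%, but its product-profile target concerns activity of 30% to 80%, and its sample-size figure covers deficient and intermediate activity together. Neither is specific to severe deficiency, so 90% and 99% are added as an assumed range.
- r, the share of misses that vanish on retest. This is an assumption; the documents give no value.
- Specimens are taken as independent with a common sensitivity, and discordance as disagreement at the cut-off.

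Formula: P(no miss remains) = (1 - (1 - s)(1 - r))^n.

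| s | r = 0 (first results) | r = 0.25 | r = 0.5 |
|---|---|---|---|
| 0.90 | 0.90^20 = 0.122 | 0.925^20 = 0.210 | 0.95^20 = 0.358 |
| 0.95 | 0.95^20 = 0.358 | 0.9625^20 = 0.466 | 0.975^20 = 0.603 |
| 0.99 | 0.99^20 = 0.818 | 0.9925^20 = 0.860 | 0.995^20 = 0.905 |

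At least one miss occurs with probability 1 - 0.358 = 0.642 at s = 0.95, and 1 - 0.122 = 0.878 at s = 0.90. The exact 95% lower limit for 20/20 is 0.025^(1/20) = 0.832. A device with exactly that sensitivity reaches 20/20 with probability 0.025 on first results, and (1 - 0.168 × 0.5)^20 = 0.172 at r = 0.5.

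The stakes would therefore be real if repeats counted. The remaining question is whether the plan lets them count.

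**What the text allows.**

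1. *Specimen.* The criterion names fingerstick blood for the POC test. The retest uses stored venous blood, and the leftover aliquots are frozen, while the device is described for fresh blood. A POC retest therefore does not produce the result that the criterion judges.
2. *Purpose.* Each repeat rule has its own trigger. The invalid-stick rule supplies a missing result. The duplicates rule deals with an unreliable reference value without regard to the POC result. The index-reference rule is given a different aim: whether the disagreement repeats. That question presupposes that the first disagreement remains on record.
3. *Reporting.* Section 5.1.2 names performance characteristics and the additional results as two items. If the repeats were merged into the performance figures, the second item would have no separate place. A miss later overturned would be visible in the report.
4. *Meaning of discordance.* The sentence before the index-reference rule uses the word for a numerical gap of more than 2 IU/g, and section 8.1.2 sets agreement limits of ±2.0 U/g Hb. On a numerical reading, some correct detections are retested and some misses are not. The one-sided selection then no longer holds as described, and r does not apply to every miss.
5. *Pointe half.* Cases are defined by Pointe, so this half is met almost by definition. It can still fail without a repeat: at the boundary (<30% against ≤30%), or if the two initial duplicates fall on either side of the cut-off. It therefore does not imply that repeats count.
6. *Blinding.* The initial reference values exist before any index-reference discordance can be seen. When first results stand, an unblinding repeat request cannot alter the primary result.

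**The case for a change.** The strongest argument for a change is that an inferred purpose is not an analysis rule. The data are meant for regulatory submission, a miss is more likely than not at 95% sensitivity or below, and one sentence saying that first results are primary would cost nothing. The reporting rule relies on a WHO specification, and the sensitivity calculation on published recommendations for evaluating G6PD tests. Neither can be consulted here, so they cannot be assumed to close the gap.

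Part of this stands. No section says that first results are primary, which assay is repeated after an index-reference discordance, how discordance is defined, or how the Pointe duplicates are combined. The arithmetic is also correct under its stated r.

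It does not show, however, that the plan as written would yield a different primary result. To rescue a miss, an analyst would have to put a stored venous POC value in place of the fingerstick value that 8.1.1 names, or override an initial reference value with a repeat done to check reproducibility. Neither step is authorised by the text.

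Retesting some concordant specimens as well would show whether detections repeat, but would change no primary result once first results stand. Removing the Pointe clause would change no result either, and the width of the interval around 20/20 is already disclosed by the planned 95% limits.

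**Conclusion.** The concern does not call for a change. The plan leaves one analysis rule unwritten, but the named specimen, the stated purpose of the retest and the separate listing of its results all lead to the same rule: the first valid fingerstick result and the initial reference result decide the criterion, and index-reference retests are reported alongside. Writing this down would record what the plan already implies.

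The possible effect, a rise from 36% to 60% in the chance of no miss at 95% sensitivity with 20 cases, arises only if repeats replace first results, discordance means disagreement at the cut-off, and half of the misses are overturned. The first condition goes against the text, the second is one of two plausible readings, and the third has no basis in the documents. At 99% sensitivity the same assumptions move the chance only from 82% to 90%.

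This conclusion rests on the protocol text alone and assumes that the cited WHO specification does not direct analysts to replace first results with repeats.
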